2.2.5 Safety Outcome Measures

The primary safety outcome measure is:

- Proportion of patients who complete 24 weeks of combination treatment on pirfenidone at a dose of 1602–2403 mg/d and nintedanib at a dose of 200–300 mg/d.

Secondary safety outcome measures are:

- Proportion of patients who discontinue pirfenidone, nintedanib, or both study treatments because of adverse events before the Week 24 visit,
- Total number of patient days of combination treatment with pirfenidone at a dose of 1602–2403 mg/d and nintedanib at a dose of 200–300 mg/d,
- Total number of days from the initiation of combination treatment to discontinuation of pirfenidone, nintedanib, or both study treatments,
- Frequency and timing of Adverse Events (AEs) and Serious Adverse Events (SAEs).

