4. STATISTICAL METHODS

This is a safety and tolerability study, not designed to assess efficacy, comprising only one treatment group. There are no formal statistical hypothesis tests to be performed, and there will be no adjustments for multiplicity of endpoints or within-subgroups comparisons. Efficacy analyses will be limited to descriptive statistics.

Categorical data will be summarized using frequencies and percentages (including a category for missing, if appropriate).

Continuous endpoints will be summarized using descriptive statistics (mean, standard deviation, minimum, 25th and 75th quartiles, median, and maximum).

Where data will be presented over time, e.g. Baseline, Week 12, Week 24, and early discontinuation visit, an end of treatment visit (EOT) will be added. This will include Week 24 data for patients who completed 24 weeks of combination treatment and data from the early discontinuation visit for patients who prematurely discontinued from combination treatment.

Other analysis methods will be specified below, where applicable. All data recorded in the electronic Case Report Form (eCRF), as well as derived data that will be used in analyses, will be listed.

Analyses will be presented for the total population, together with geographic region, i.e. US and non-US patients. Results for US and non-US will be presented as additional columns or additional blocks within the outputs of the total population.

Percentages will be based on the total population or on the number of patients in the respective geographic region, if not otherwise specified.

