4.7.3 Adverse Events

Verbatim descriptions of adverse events (AEs) will be mapped to a preferred term (PT) and system organ class (SOC) using the Medical Dictionary for Regulatory Agencies (MedDRA®). MedDRA version 19.0 or higher and related SMQ lists (see below) will be used for coding.

AEs will be graded according to the National Cancer Institute Common Terminology Criteria for Adverse Events (NCI CTCAE), Version 4.03. For AEs of varying severity, the most severe grade as documented on the eCRF will be used in the summaries.

According to the protocol, after informed consent has been obtained but prior to initiation of combination treatment on Day 1, only SAEs caused by a protocol-mandated intervention should be reported.

After initiation of combination treatment at or after the Baseline visit, all adverse events will be reported until 28 days after the last dose of study drug. After this period, the Investigator should report any SAEs that are believed to be related to prior study drug treatment.

An AE that started or worsened on the day of initiation of combination treatment through 28 days after the date a subject completed or early discontinued from combination treatment period' as per eCRF 'Study drug completion/Early Discontinuation' will be considered treatment emergent.

The analysis of AEs will focus on treatment-emergent AEs (TEAE), but all AEs will be listed. For AEs that might occur after initiation of investigational pirfenidone up to start of combination treatment or more than 28 days after the end of combination treatment a separate listing will be provided.

Classifications of seriousness, severity and causality are described in the protocol sections 5.2 and 5.3.

An overview of patient safety profile will present the number and proportion of patients experiencing

- all and related treatment-emergent adverse events (TEAE),
- all and related serious treatment-emergent adverse events (serious TEAE),
- all and related severe TEAE,
- all and related TEAE of special interest (AESI) (MedDRA Preferred term for STIAMP - 'Suspected transmission of an infectious agent via product' or SMQ: 'Drug related hepatic disorders – severe events only (SMQ)'),
- all and related gastrointestinal (GI) disorders (SOC: Gastrointestinal disorders),

**Pirfenidone and nintedanib — F. Hoffmann-La Roche Ltd
Statistical Analysis Plan MA29895, Version 2.0, final, 17 May 2017**

27

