The following categories of TEAEs as presented in the overview will be summarized by system organ class (SOC) and preferred term (PT):

- all and related treatment-emergent adverse events (TEAE),
- all serious treatment-emergent adverse events (serious TEAE),
- all non-serious treatment-emergent adverse events (non-serious TEAE),
- all severe (Grade 3 – 5) treatment-emergent adverse events (severe TEAE),
- all TEAEs resulting in hospitalization or prolonged hospitalization

Similar summary presentations will be provided for patients with TEAEs leading to dose modification.

Frequencies and percentages of patients experiencing (at least) one event in the respective category will be presented by decreasing frequencies. If patients have more than one AE within a SOC or PT they will be counted only once for the respective SOC or PT. Total numbers of TEAEs will be provided for each SOC and overall.

Special interest in this study will be on assessment of treatment discontinuation. Therefore, TEAEs leading to treatment discontinuation will be summarized for TEAEs leading to discontinuation of any drug, and for TEAEs leading to discontinuation of both treatments, to pirfenidone alone or to nintedanib alone. Additional presentations for the following categories of TEAEs leading to treatment discontinuation will be presented:

- Serious TEAEs).
- GI event,
- Photosensitivity reaction or rash
- TEAEs by intensity.

All TEAEs indicating "Action taken with pirfenidone/nintedanib due to SAE/AE" = "Drug withdrawn" in the eCRF will be included in these summaries.

Numbers and frequencies of patients with TEAEs by most extreme CTCAE Grade will be provided for any TEAEs and for each SOC and PT. In case the most extreme intensity is missing, it will be replaced by the initial intensity. If both most extreme and initial intensity are missing, AE will be included in the summaries for grade 3 to 5 AEs (i.e. in the total column) and a column for "missing" will be added.

The timing of TEAEs will be assessed by presenting numbers of patients with TEAEs occurring in the first 28 days (Days 0 – 28), from Day 29 to Day 84 (Weeks >4 - 12), and for the total study period by SOC and PT.

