Further, Kaplan-Meier curves for time to onset of first adverse event of the most relevant related TEAEs will be provided. These will include the following PTs or baskets (as defined above): Nausea, Diarrhoea, GI disorder basket, Weight decreased, Fatigue, Decreased appetite, photosensitivity or rash basket.

All adverse event data will be listed by patient number and study day of onset. Separate listings will be provided for TEAEs leading to treatment discontinuation, serious TEAEs (STEAEs), adverse events of special interest (AESIs), TEAEs leading to dose modification, TEAEs leading to hospitalization, severe (Grade 3 – 5) TEAEs and deaths.

Non-treatment-emergent AEs (i.e. AEs that start prior to first administration of combination treatment and do not worsen at/after combination treatment, or AEs that start more than 28 days after last dose of combination treatment) will be listed separately.

The following additional analyses will be performed for the purpose of fulfilling the Clinical Trial Registry (CTR) requirements:

- Both Serious Adverse Events and ‘Other’ Adverse Events will be summarized by MedDRA preferred term.

An adverse event is considered ‘Serious’ whether or not it is a TEAE. An adverse event is considered in the ‘Other’ category if it is both, a TEAE and is not serious.

For each Serious AE and ‘Other’ AE, and for each term the following are provided:

- The number of subjects at risk of an event;
- The number of subjects who experienced each event term;
- The number of events experienced.

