4.9 VISIT WINDOWS

Visit windows will be applied to vital signs and laboratory data and the derived visits will be used in the by-visit summarizations. If multiple observations fall within the same visit window, the observation with the most extreme value will be used in the analysis, if not stated otherwise.

For presentation of vital signs, laboratory tests, exposure and pulmonary function test results, an end of treatment (EOT) visit will be defined. This will include Week 24 data for patients who completed 24 weeks of combination treatment and data from the early discontinuation visit for patients who prematurely discontinued from combination treatment.

Table 5 Visit Windows for vital signs and laboratory data

Analysis Visit [AVISITN]	Target Day	Window (Study Days)
Baseline [0]	1	Last valid assessment prior to start of combination treatment
Week 1 [1] – lab data only	7	2 to 10
Week 2 [2]	14	11 to 17 (2 to 21 vital signs)
Week 3 [3] – lab data only	21	18 to 24
Week 4 [4]	28	25 to 42 (22 to 42 vital signs)
Week 8 [8]	56	43 to 70
Week 12 [12]	84	71 to 98
Week 16 [16]	112	99 to 126
Week 20 [20]	140	127 to 154
Week 24 [24]	168	155 to 174
Early discontinuation [25]	Not applicable	As occurred
End of treatment (EOT) [26]	Not applicable	As occurred
Follow-up [28]	Combination treatment end date + 28	As occurred

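### The TEAE timing table has no window after Day 84 and no person-time, so it can neither isolate late onset nor compare risk between periods

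*SAP*

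**What the plan says.** Section 2.2.5 of SAP Version 2.0 lists as a secondary safety outcome: "Frequency and timing of Adverse Events (AEs) and Serious Adverse Events (SAEs"). The amendment rationale of Version 2.0 records that an analysis of TEAE timing was added because the previous version had none.

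Section 4.7.3 supplies two summaries:

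- **A table** "presenting numbers of patients with TEAEs occurring in the first 28 days (Days 0 – 28"), then "from Day 29 to Day 84 (Weeks >4 - 12), and for the total study period by SOC and PT".
- **Curves:** "Kaplan-Meier curves for time to onset of first adverse event of the most relevant related TEAEs will be provided". The items are "Nausea, Diarrhoea, GI disorder basket, Weight decreased, Fatigue, Decreased appetite, photosensitivity or rash basket".

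The time frame comes from elsewhere in the SAP. Table 5 in section 4.9 gives "Week 24 [24] 168 155 to 174", so planned treatment ends at about Day 168. Section 4.7.3 counts an event as treatment-emergent "through 28 days after the date a subject completed or early discontinued from combination treatment period".

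The sentence on the table asks for numbers of patients and sets no denominator. The general rule in section 4 is: "Percentages will be based on the total population or on the number of patients in the respective geographic region, if not otherwise specified".

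**The concern.** In a study whose purpose is safety and tolerability, the timing table is the only timing summary that reaches every system organ class (SOC) and preferred term (PT). It has two weaknesses.

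1. It stops separating time at Day 84, halfway through planned treatment. Events after that day enter the total column but cannot be told apart there.
2. The second window is twice as long as the first, and neither is related to time at risk. Read side by side, the two counts suggest a trend that may only reflect window length.

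At stake is whether the report can say when serious events, hepatic AE terms and the many terms without a Kaplan-Meier curve tend to start, and in particular whether some start late.

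**Working it through.** **Inputs from the SAP.** Windows: Days 0-28 and 29-84 (section 4.7.3). Day 1 is the first day of combination treatment, so Day 0 does not exist (section 4.2.1). Treatment runs to Day 168 (Table 5), with a 28-day TEAE tail (section 4.7.3). N = 80, with 85% assumed to complete (section 2.3).

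**Assumed, because the SAP gives no event rate.** A constant TEAE rate such that 10%, 30% or 60% of patients have at least one event per 28 days. Discontinuation is exponential. Events are counted on treatment only.

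**1. The plan's own figure.** 28/7 = 4 and 84/7 = 12, so Weeks >4 to 12 agrees with Days 29-84.

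**2. Time without a window.**
- On treatment: 168 − 84 = 84 days, and 84/168 = 50%.
- Including the tail, for a completer: 168 + 28 = 196 days; 196 − 84 = 112 days, and 112/196 = 57%.

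**3. Can the late count be obtained from the total?** The text does not limit the windows to first onset, so a patient may appear in more than one. Suppose the total is 40, the early count 30 and the middle count 20. The early and middle patients together may already make up all 40, so the number with an event after Day 84 may be 0. Each of the 40 may also have had a late event, so it may be 40. The table allows anything from 0 to 40.

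**4. Effect of window length.**
- Discontinuation rate: λ = −ln(0.85)/168 = 0.00097 per day.
- Event rate at 30% per 28 days: μ = −ln(0.70)/28 = 0.01274 per day.
- Expected patients with at least one event in a window that starts at a and lasts w days: 80 × exp(−λa) × [μ/(μ+λ)] × [1 − exp(−(μ+λ)w)].
- Days 1-28: 80 × 1 × 0.929 × 0.319 = 23.7.
- Days 29-84: 80 × 0.973 × 0.929 × 0.536 = 38.8. Ratio 1.64.

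| Assumed rate per 28 days | Days 1-28 | Days 29-84 | Ratio |
|---|---|---|---|
| 10% | 7.9 | 14.4 | 1.83 |
| 30% | 23.7 | 38.8 | 1.64 |
| 60% | 47.5 | 64.2 | 1.35 |

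With completion between 75% and 95%, the ratio lies between 1.32 and 1.88. The underlying risk is constant throughout.

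**5. Effect of dropout.** Patients still on treatment: 80 × exp(−28λ) = 77.9 at Day 28 and 80 × exp(−84λ) = 73.8 at Day 84 (69 to 78 at Day 84 for 75% to 95% completion). This is small beside the effect of window length.

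**6. Which denominator repairs it?** At the 30% rate, with windows Days 1-28, 29-84 and 85-168:

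| Summary | 1-28 | 29-84 | 85-168 |
|---|---|---|---|
| Patients with an event, of those at risk at window start | 30% | 50% | 64% |
| Person-days on treatment | 2210 | 4244 | 5950 |
| Patients with an event per 1000 person-days | 10.7 | 9.1 | 7.9 |
| Expected events (μ × person-days) | 28.2 | 54.1 | 75.8 |
| Events per 1000 person-days | 12.7 | 12.7 | 12.7 |

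An at-risk denominator alone leaves a false rise. Patients divided by all person-days leaves a smaller false fall, because a patient counts once however long the window. Events divided by person-time is flat, as it should be.

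**The case against.** The strongest reply is that the table is neither the whole timing analysis nor a comparison. Several parts of that reply stand.

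- **The total column exists.** A reader might infer that events after Day 84 go unreported. They do not: they are counted in the total study period but have no window of their own.
- **The Kaplan-Meier curves carry no Day 84 limit.** They handle censoring and do not depend on window length. A reader might infer that the plan cannot show timing at all. That goes too far: the table shows early onset, and the curves cover seven related terms or baskets, including gastrointestinal events, a main area of overlap between the two drugs.
- **Hepatic laboratory toxicity is covered.** Section 4.7.6 presents Grade 3 and 4 values over time, and Table 5 has visits through Week 24 and Follow-up. The hepatic gap concerns AE terms, not liver tests.
- **Onset days are listed,** with separate listings for serious TEAEs, events of special interest and deaths. With about 80 patients this is useful, but a listing does not summarise timing.
- **Dropout matters little.** A reader might infer that dropout would pass for falling toxicity. At the plan's 85% completion, about 74 of 80 patients are still on treatment at Day 84, so this is a minor point.
- **The study is descriptive.** Section 4.7 promises no comparative statistics, and the windows are labelled with their days. But a table stated to assess timing will be read across its columns, and labels do not supply the missing late window.
- **Exposure-adjusted rates assume a constant hazard within a window,** while nintedanib is titrated over the first 15 days. This is a fair limit on interpreting the first window.

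**Conclusion.** The point holds in this form. As specified, the table gives no separate view of the second half of treatment (84 of 168 days, or 112 of 196 with the tail), and its counts cannot be used to compare risk between periods. The gap falls on serious TEAEs, the hepatic AE basket and the SOCs and PTs outside the Kaplan-Meier list. For these, a stated secondary outcome rests on this table and the listings.

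The missing window follows from the text alone. The factor of 1.35 to 1.83 rests on assumed event rates, a constant rate, 85% completion, and a patient counting in every window with an event. If the table were meant to count first onsets only, the late count would follow by subtraction and that factor would not apply; the SAP does not say so. The rule that a patient counts once per SOC or PT does not address windows.

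This should be corrected, but it is not critical: no primary estimate or confidence interval depends on it.

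**What to change.** In section 4.7.3, replace the timing windows with four that do not overlap:

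1. Days 1-28 (dropping Day 0, which section 4.2.1 does not define).
2. Days 29-84.
3. Day 85 to the date of completion or discontinuation of combination treatment.
4. From that date to 28 days later.

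End windows 1 to 3 at completion or discontinuation, so that an early discontinuer's follow-up days fall only in window 4. State that a patient counts in each window in which an event starts.

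For each window show the number of patients at risk at its start, the number with at least one event, and the person-time. If a rate is given, use events over person-time, or patients with a first event in the window over person-time up to that event. Repeat the table for serious TEAEs.

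The cost is one revised table shell, its repeat for serious TEAEs, and longer output. Onset dates and treatment dates are already collected. The rates assume a constant hazard within each window, and a footnote should say so.

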4.7.4 Deaths

Numbers and frequencies of deaths and of deaths occurring within 28 days after the last dose of combination treatment will be presented. The primary cause of death and the information on whether an autopsy was performed will be given. All information on deaths will be collected from the eCRF panel on study discontinuation.

4.7.5 Pregnancies

Pregnancy test results will be listed, presenting the visit, date and study day of pregnancy test and test result.

4.7.6 Laboratory Data

All laboratory parameters will be assessed by a central laboratory, with the exception of the results of urine pregnancy tests, which will be determined locally and will be recorded in the eCRF.

All parameters will be graded according to NCI CTCAE (CTEP 2010), version 4.03, if applicable. Laboratory parameters that cannot be graded according to NCI CTCAE version 4.03 will be assessed with respect to normal range (low, normal, high).

For laboratory parameters and specific age ranges, the upper limit of normal provided by the central laboratory might be higher than the criterion for Grade 1 in NCI CTCAE. In such cases, the definitions provided in the NCI CTCAE, version 4.03 will be followed. This means that a shift of a laboratory value above the ULN that corresponds to a grade 2 abnormality or higher will be reported as such. Grade 1 abnormalities will not be reported for such situations.

Laboratory values that are reported to be below the limit of quantification (e.g. '<2') will be considered as to be 'LOW' for presentation in shift tables, if the value (e.g. '2') equals the lower limit of normal. The value as such (e.g. '2') will be used for descriptive statistics.

The following laboratory parameters will be collected:

- Hematology: complete blood count with platelet count and automated differential, i.e. hemoglobin, hematocrit, platelet count, red blood cell count, RBC morphology, white blood cell count, absolute differential count (neutrophils, bands, eosinophils, lymphocytes, monocytes, basophils), MCH, MCHC, MCV,
- Serum chemistry: albumin, alkaline phosphatase, ALT, AST, direct bilirubin*, total bilirubin, calcium, cholesterol, creatine kinase, creatinine*, triglycerides, gamma-glutamyl transferase, glucose, lactic dehydrogenase*, magnesium, phosphorus*, potassium, sodium, urea nitrogen, serum uric acid*, and amylase, C-reactive protein (N HS)-PS* (CRP), Creatinine clearance rate*, calculated using the Cockcroft-Gault formula
- Serum pregnancy test*,
- Urine dipstick for pregnancy testing*(local).

* = for these parameters no grading as per NCI CTCAE, version 4.03 is applicable.

Hemoglobin A1c (HbA1c) was planned to be collected according to the initial version of the Clinical Study Protocol (CSP), but was removed in Amendment 3 of the CSP as not specifically relevant for this patient population. HbA1c values are continuously reported by the central laboratory, but will not be presented in any summary presentations. HbA1c values will only be listed.

**Pirfenidone and nintedanib — F. Hoffmann-La Roche Ltd
Statistical Analysis Plan MA29895, Version 2.0, final, 17 May 2017**

Clinical laboratory values will be presented separately for CTCAE-gradable and non-CTCAE gradable parameters by laboratory panel (hematology, serum chemistry).

Serum or urine pregnancy data will only be listed.

For laboratory analyses, visits will be assigned to visit windows as described in Section 4.9. This will also be valid for possible unscheduled visits. In case that multiple evaluable assessments occur within the same visit, the most extreme value will be used for analyses.

The following summaries will be prepared:

For each laboratory parameter, descriptive statistics of laboratory values at each scheduled visit (derived as described above), and absolute changes from baseline to post-baseline will be presented.

Shift tables presenting changes from baseline to worst CTCAE grade, in the indicated direction, will be provided for CTCAE-gradable parameters. These changes will also be expressed as shifts of 1 to 4 grades, 3 to 4 grades and 4 grades. If no CTCAE grade is available for a specific laboratory variable, shift tables will present worst changes with respect to normal range category (low, normal, high).

For CTCAE-gradable parameters, numbers and percentages of patients with laboratory values of Grade 3 and 4 will be presented over time. Further, the total number of visits with Grade 3/4 elevations, as well as the number and percentages of patients with Grade 3/4 elevations for each parameter will be provided.

Liver abnormalities (total bilirubin, alkaline phosphatase, ALAT (SGPT), ASAT (SGOT)) of Grade 3 and 4 will be presented showing numbers and percentages of patients for each parameter separately, as well as in combination with at least one of the other parameters elevated post-baseline. Line graphs will also be provided.

All laboratory data will be listed.

